#### 4.3.3. Safety analysis

An overview of adverse events will be presented and will include the number and percentage of patients in the different categories indicated in section 4.8.2.

The following information will be listed by treatment group for review at each meeting:

- Serious adverse events
- Withdrawals due to adverse events
- Other early study withdrawals with reason
- Severe adverse events
- Adverse events

Adverse event summaries will include all available data and will not be limited just to data through Week-4.

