#### **11.1.2 Safety**

In addition to assessing efficacy, the study objectives also include further evaluation of the safety of a range of doses of NT-814 in women with menopausal symptoms. Regarding estimation of differences in AE rates from placebo for a given dose group, Table 11-1 (computed via normal approximation to the binomial distribution) shows the half-width of 95% confidence intervals for difference between a pair of treatment groups. This indicates the precision for such estimation for several example cases. The DRC will use these confidence intervals to assist in their consideration of increasing the sample size of those doses which achieve target levels of HF frequency and severity reduction in order to better assess safety. Criteria for such considerations will be described more fully in the DRC Charter.

**Table 11-1 Estimates of 95% confidence interval half-widths for a representative range of treatment group differences in incidence of adverse events and sample sizes**

OBSERVED between-group difference in percentage	95% confidence interval half-width for indicated N/group and OBSERVED percentage point difference from placebo		
	N=30	N=40	N=50
15 - 5 = 10	15	13	12
25 - 5 = 20	17	15	13
35 - 5 = 30	19	16	15
20 - 10 = 10	18	15	14
30 - 10 = 20	20	17	15
40 - 20 = 20	21	18	16
30 - 20 = 10	22	19	17
40 - 20 = 20	23	20	18
50 - 20 = 30	23	20	18

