### 4.3. Interim Analyses

The first IA will be conducted after efficacy data from frequency and severity of HF is collected through Week 4 from 30 patients randomized in equal proportions to the four NT-814 doses and placebo.

Based on DRC review of the IA results, randomization ratios for subsequent enrolled patients may be changed to optimize the allocation of subjects to doses with target levels of weekly average daily HF frequency reduction from baseline of 6 and 8; and HF severity reduction from baseline of 0.66 and 0.88 (Study RELENT-1). Adaptive design algorithm will be based on Bayesian Emax dose-response modelling [1] and / or T-statistic adaptive dose-finding design [2]. The DRC will have dose assignment recommendations by each of those adaptive dose-finding algorithms and assign the randomization ratio that best integrates the objectives of the trial and the adaptive design results. Randomisation ratio recommendations will also take into consideration emerging safety findings as well as the need to allocate sufficient subjects to a dose of interest to enable an adequate assessment of safety to be made.

Subsequent IA's will be conducted similarly, after Week 4 data from each cohort of ~30 additional patients become available.

The DRC will evaluate stopping criteria per the IA algorithms as described in Appendix B of the protocol and decide on stopping assignment of subjects to specific doses or stopping the trial for an efficacy conclusion and dose choice for subsequent study or futility.

The review of efficacy will be based only on the frequency and severity of HF recorded by subjects in the electronic diary (eDiary).

The review of safety will be based on adverse event and early withdrawal information.

For each IA, a cut-off date will be applied such that data will be included until the date the last patient in the analysed cohort completes the Week 4 visit.

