#### 4.8.2. Adverse Events

Adverse events will be coded using MedDRA Version 21.1 and displayed in tables and listings using SOC and PT.

Analyses of adverse events will be performed for those events that are considered treatment emergent (TEAE), where treatment emergent is defined as any adverse event with the onset date is on or after the date and time of first dosing with randomised study treatment. Any adverse event with an onset date earlier than the first dosing with randomised study treatment will be considered as a pre-treatment adverse event. In case there is any missing or incomplete onset date, the adverse event will be classified as treatment-emergent if the partial adverse event onset date/time information does not indicate that the adverse event started prior to the date and time of first dosing with study treatment. No imputation of adverse event dates/times will be performed.

If a subject experiences more than one AE with the same preferred term, that preferred term will be counted only once within summaries. It will be assigned the highest observed severity and the strongest relationship to study treatment among those events for the tables in which those characteristics are summarised.

An overview of adverse events will be presented and will include the number and percentage of patients with at least one:

- Treatment emergent adverse events
- Treatment emergent adverse events related to IMP
- Serious treatment emergent adverse events
- Treatment emergent adverse events leading to treatment discontinuation
- Treatment emergent adverse events leading to study discontinuation
- Treatment emergent adverse events leading to Death
- Severe treatment emergent adverse events

The number and percentage of subjects with the following adverse events will be presented by SOC and PT:

- Treatment emergent adverse event
- Serious treatment emergent adverse event
- Treatment emergent adverse event related to IMP
- Treatment emergent adverse event leading to treatment discontinuation
- Treatment emergent adverse events leading to study discontinuation

In addition, the treatment emergent adverse events will be summarized by SOC, by PT and by severity and by relationship to study treatment. For a patient with more than one occurrence of the same adverse event in a particular SOC/PT, only the adverse event with the most severe intensity and / or most extreme relationship to the study drug will be considered.

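### Interim adverse event percentages are crude over unequal follow-up, so arms are not comparable once the randomisation ratio has become unequal

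*SAP*

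**What the plan says.** SAP 4.3.3 states that the interim AE overview "will include the number and percentage of patients in the different categories indicated in section 4.8.2". SAP 4.8.2 defines those categories as subjects with at least one event of the given type, and for repeated events says "that preferred term will be counted only once within summaries". On the time window, SAP 4.3.3 says: "Adverse event summaries will include all available data and will not be limited just to data through Week-4".

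The cut-off in SAP 4.3 is a calendar date: "data will be included until the date the last patient in the analysed cohort completes the Week 4 visit". On timing: "Subsequent IA's will be conducted similarly, after Week 4 data from each cohort of ~30 additional patients become available".

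Four design features bear on follow-up:
- The ratio starts at 1:1:1:1:1 and may change after the first interim review (SAP 2.2).
- Active doses may be reduced or discontinued (SAP 2.2; Protocol 9.1).
- Placebo allocation continues throughout (Protocol 8.6), and so does recruitment during the interims (Protocol 11.2).
- AEs are collected to the final visit, about 16 weeks after randomisation (Protocol 10.5.4 and 8.6.2).

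Neither SAP 4.3.3 nor 4.8.2 specifies follow-up per arm, a common window or a time-to-first-event estimate. On use, SAP 4.3 says that ratio recommendations also consider emerging safety findings. Protocol 11.1.2, referring to intervals for differences in AE percentage from placebo, says: "The DRC will use these confidence intervals to assist in their consideration of increasing the sample size of those doses". The rest of that sentence limits this to doses that reach the target hot flush reductions, for the purpose of assessing safety better.

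**The concern.** The percentage of subjects with at least one event can only rise with time observed. While allocation is equal, every arm has the same mix of long and short follow-up. Once allocation is unequal, a closed dose holds only early entrants, and a dose with a raised share holds many recent ones. Arms with identical AE risk then show different crude percentages: higher on the closed dose and lower on the favoured one.

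The adaptive efficacy models do not share the problem, because they use the change at Week 4. Safety is the part of the interim package without a common time point. At stake is the DRC's reading of the AE profile of one dose against placebo while it is choosing ratios and deciding whether to add subjects to a dose.

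**Working it through.** **The plan's own figure.** The documents give no follow-up by arm at an interim. The related figure is Protocol Table 11-1, with half-width = 1.96 × √[p1(1−p1)/n + p0(1−p0)/n]. For 15% against 5% this gives 14.97, 12.96 and 11.60 points at n = 30, 40 and 50, against 15, 13 and 12 stated. In all, 24 of 27 cells reproduce. The sixth row (21, 18, 16) does not fit its label of 40 against 20 but does fit 40 against 10, a separate labelling point. The table spans 12 to 23 points.

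**Inputs from the documents.** Appendix B assumes 5 subjects per week and a 6-week lag. Interims come after each 30 subjects, and follow-up is capped at 16 weeks. Interim k then has its cut-off at week 6k + 4. A first ratio change takes effect at week 12, with 60 randomised (12 per arm).

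**Assumptions, because the documents give no values.** Two doses are closed after the first interim, placebo stays at 20% (the share in Appendix B's simulations, not fixed for the trial) and two doses take 40% each. Every arm has the same 30% risk by Week 16 with constant hazard, so λ = −ln(0.7)/16 = 0.0223 per week.

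**Third interim, week 22.**
- The 12 early women per arm entered in weeks 0 to 12. Half have 16 weeks of follow-up and half have 10 to 16, so the mean is (16 + 13)/2 = 14.5 weeks. Their expected percentage is (30.0 + 25.1)/2 = 27.55.
- Later entrants (weeks 12 to 22) have a mean of 5 weeks and an expected 10.36%.
- Closed (12 women): 27.6%.
- Placebo (12 early + 10 late): (12 × 27.55 + 10 × 10.36)/22 = 19.7%. Mean follow-up is (12 × 14.5 + 10 × 5)/22 = 10.2 weeks.
- Favoured (12 early + 20 late): (12 × 27.55 + 20 × 10.36)/32 = 16.8%. Mean follow-up is (12 × 14.5 + 20 × 5)/32 = 8.6 weeks.

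| Case (equal true risk) | Closed | Placebo | Favoured |
|---|---|---|---|
| First interim, 30% risk | 10.4 | 10.4 | 10.4 |
| Second interim, 30% risk | 19.7 | 15.9 | 13.6 |
| Third interim, 30% risk | 27.6 | 19.7 | 16.8 |
| Third, 50% risk | 46.5 | 33.9 | 29.2 |
| Third, 70% risk | 66.0 | 49.5 | 43.3 |
| Third, 30% risk, all events in weeks 0–4 | 30.0 | 27.4 | 26.5 |
| Third, 30% risk, analysed cohort only | 27.6 | 23.2 | 21.0 |

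If only the analysed cohort is counted, the second interim shows no gap, because its 60 women all entered before the ratio changed. With no closure and one dose at 40%, at 50% risk the third interim gives 36.6% (reduced doses), 33.9% (placebo) and 29.2% (favoured).

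**Against sampling error.** At the third interim with 30% risk, the 95% half-width is about 21 points for favoured against placebo (32 and 22 women) and about 30 for closed against placebo (12 and 22).

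**Candidate corrections, third interim, equal 30% risk.**
- First events per 100 subject-weeks at risk: 2.23 in every arm at constant hazard. If all events fall in weeks 0–4, it is 2.80 (closed), 3.58 (placebo) and 4.06 (favoured), a false excess of 4.06/2.80 = 1.45 for favoured against closed.
- Percentage with onset in the first 4 weeks, among women randomised at least 4 weeks earlier: 1 − 0.7^(4/16) = 8.5% in every arm at constant hazard, and 30.0% in every arm if all events fall in weeks 0–4.

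**The case against.** The strongest reply is that the effect is conditional and small where it matters most. That is largely right. The first interim is untouched, and nothing happens while the ratio stays equal. The favoured-against-placebo part needs a favoured share above placebo's: if placebo and the continuing doses share the freed places equally, it is zero. Closing two doses at the first opportunity is also an extreme case. In the non-flat scenarios of Appendix B Table 1a, no dose averages fewer than 13.9 subjects.

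A reader might set the gap between closed and favoured doses, 27.6 − 16.8 = 10.8 points, beside the 10-point differences in Table 11-1. Those are differences from placebo, so the comparison is not like for like. A reader might also infer that the crude intervals close doses or set ratios. Protocol 11.1.2 gives them a narrower use, in considering more subjects for doses that already meet the efficacy targets, and the COMPASS recommendations use efficacy only.

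The DRC is unblinded and receives AE listings by treatment group and subject allocation, so it could notice the imbalance. The DRC Charter is not among the documents, and the marking of which tables go to each interim cannot be read in the available text, so exposure Table 14.1.5 may be supplied. The SAP also describes blinded data review decisions as already made, so rewording it may come too late to change any interim table.

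These points limit the impact. They do not make the percentages in SAP 4.3.3 comparable after a change to unequal allocation.

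**Conclusion.** The concern holds in a limited form. After a change to unequal allocation, the specified summary does not compare like with like. In the worked scenario at the third interim it misplaces a closed dose by about +8 points and a favoured dose by about -3 points against placebo. These fall to about +2.6 and just under -1 if all events occur in weeks 0–4, and to +4.4 and -2.2 if only the analysed cohort is counted.

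The risk level, hazard shape and revised ratios are assumptions. At 50% risk the gaps are +12.6 and -4.7. In the 30% scenario they are below every half-width in Table 11-1, but they keep the same direction at later interims, which random error does not. The final analysis is largely unaffected, since follow-up is then 16 weeks in every arm apart from withdrawals.

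The documents do not support the stronger inference that the design makes a favoured dose look safer than placebo whatever happens, or that it conceals harm. Minor to moderate priority.

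**What to change.** In SAP 4.3.3, keep the all-data listings and overview, and add to the interim AE overview:
1. Mean follow-up and total person-weeks per arm.
2. The percentage with an event with onset in the first 4 weeks, among subjects randomised at least 4 weeks before the cut-off, including those who left earlier. Alternatively, Kaplan-Meier cumulative incidence of first event at fixed times.
3. A statement that between-arm AE comparisons at interims use the figure in item 2, not the crude percentages.

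Also state whether the denominator is all subjects randomised by the cut-off date or only the analysed cohort.

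Events per subject-week should not be the main comparison. It is unbiased only under constant hazard and reverses the bias when events come early.

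The cost is a few lines of SAP text and extra columns in one interim table, and the dates needed are already collected. The drawback is that the 4-week figure leaves out recently randomised women, who remain in the listings. If the interims have already taken place, report follow-up per arm wherever their AE percentages are described in the study report.

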#### 4.4. Subject Disposition

A tabulation of subject disposition will be provided on the Screen Analysis Set and will include:

- the number of patients screened,
- the number of screen failures,
- the number of patients randomized,

- the number of patients who received randomised treatment.

A tabulation of randomised treatment and study completion/discontinuation status will be provided on the Randomised Analysis Set and will include

- the number of patients randomized,
- the number of patients who received randomised treatment.
- the number of patients who completed the treatment
- the number of patients who withdrew prior to completing the treatment, and reasons for withdrawal,
- the number of patients who completed the study,
- the number of patients who withdrew prior to completing the study, and reasons for withdrawal.

An overview of the number of patients included in each population together with reason for screen failure or exclusion from populations will be produced for the Randomised Analysis Set.

A by-subject listing of study and treatment completion information, including the reason for premature study withdrawal, if applicable, will be presented. All study and visit dates will be also listed.

The number of patients by country, and by site within each country will also be summarized on the Safety Analysis Set.

## **4.5. Demographic and Baseline Characteristics**

### **4.5.1. Demographics characteristics**

Demographics information will be summarized by treatment group using descriptive statistics for the Safety Analysis Set and will include:

- Age at screening (years)
- Ethnicity
- Race
- Region
- Weight [kg]
- Height [cm]
- Body Mass Index (BMI) [kg/m^2]: defined as  $\text{Weight (kg)} / (\text{Height (m)})^2$

Weight collected at baseline (Visit 3) and height collected at Visit 2 will be used.

The following conversions will be applied:

$\text{Weight (kg)} = 0,45359237 * \text{Weight (lb)}$

$\text{Height (cm)} = 2,54 * \text{Height (Inches)}$

Demographic data will also be provided in data listings.

#### 4.5.2. Baseline Disease characteristics

Baseline Disease characteristics will be summarized by treatment group using descriptive statistics for the Safety Analysis Set and will include:

- Duration of menopause (years) as continuous summary and in categories [ $<5$  years;  $\geq 5$  to  $<10$  years;  $\geq 10$  years].
- Age at menopause Onset (years) as continuous summary and in categories [ $<50$  years;  $\geq 50$  years].
- Menopause history

#### Computation of Duration of menopause and Age at menopause onset

The CRF requests to record date of the last menstrual period. However, a partial date is accepted.

Imputation will be performed in case the date of the last menstrual period is partial:

- If only Day is missing, it will be imputed as 1st of the month
- If day & month are missing, it will be imputed as 1st January
- If year is missing, no imputation will be done.

After imputation, the date of the last menstrual period must be more than 6 weeks prior to the date of Informed Consent (IC).

Duration of menopause (y) = (Informed Consent date – Last menstrual period date) + 1/365.25

As year of birth is not collected, it will be estimated using:

Year of birth = Informed Consent year – Age on day of screening

Age of menopause (y) = Last menstrual period year – Year of Birth

Baseline data will also be provided in data listings.

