#### **7.2 Inclusion Criteria**

Subjects must meet all the inclusion criteria listed below.

1. Females aged 40 to 65 years, inclusive, at Screening Visit 1.
2. Able to understand and comply with the requirements of the study and give informed consent.
3. Postmenopausal, defined as: (i) at least 12 months of spontaneous amenorrhea, or (ii) at least 6 months of spontaneous amenorrhea with serum FSH levels > 40 mIU/ml and a serum oestradiol concentration of < 30 pg/mL, or (iii) at least 6 weeks postsurgical bilateral oophorectomy with or without hysterectomy.
4. Body mass index between 18 and 38 kg/m^2, inclusive, at Screening Visit 2.
5. Negative urinary pregnancy test at Screening Visit 2.
6. In good general health, in the opinion of the investigator, based on the medical history, physical examination, 12-lead ECG, vital signs and clinical laboratory tests assessed at Screening Visit 2.
7. Subject has completed the paper diary for at least 6 days between Screening Visits 1 and 2 and has recorded an average of at least 8 moderate or severe hot flushes per day (including night-time) over the last 5 days that the paper diary was completed (assessed at Screening Visit 2).

---

 Durations are relative to screening visit 1

 Subjects who do not clearly fall into 1 of the 3 defined categories, but who are hormonally post-menopausal (serum FSH levels > 40 mIU/ml and a serum oestradiol concentration of < 30 pg/mL) and of an appropriate age, may also be considered for inclusion.

8. Subject has completed the electronic diary for at least 9 days between Screening Visit 2 and Day 1 and has recorded an average of at least 7 moderate or severe hot flushes per day (including night-time) over the last 7 days that the eDiary was completed (assessed at the Baseline Visit).

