#### 4.2.8. Study Day

Study Day is the number of days since the date of the administration of the first dose of randomised study treatment (Study Day 1). If the assessment date is after the date of the first dose, the study day is calculated as (date of assessment - date of the first randomised treatment intake date+ 1). If the assessment date is prior to the date of the first dose, the study day is calculated as (date of assessment - date of the first randomised treatment intake date). All assessments prior to Study Day 1, including the Screening visits 1 and 2, will have negative study days (i.e. no Day 0).

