**Table 3 Exposure variables definitions**

Variables	Definitions
Duration of dosing (days)	Last dose of randomised blinded treatment – first dose of randomised blinded treatment +1
Duration of dosing (weeks)	(Last dose of randomised blinded treatment – first dose of randomised blinded treatment +1) / 7

Study treatment compliance (%)	
<math>100 * (\text{total number of capsules taken}) / (\text{total number of capsules planned to be taken})</math>
 
Note: number of capsules planned to be received is 4*duration of dosing (in days).
 
Total number of capsules taken is calculated using the eCRF pages ‘Drug Accountability’ and ‘IMP dispense/administration’, based on the fact that each weekly card contains 32 capsules and four weekly cards will be dispensed at each of baseline, week 4 and week 8. Thus, one visit dispensed kit contains <math>32*4=128</math> capsules. At subsequent Visits (Weeks 4, 8 and 12) the number of capsules remaining within the 4 weekly cards is recorded and the number of capsules taken = <math>128 - \text{Number of capsules remaining in the 4 weekly cards}</math>.
 
In the event that the subject doesn’t return some or all of the 4 weekly cards at Week 4, 8 or 12, it will not be possible to determine the number of capsules taken, so protocol medication adherence taken will be set as missing. In the event that more than one kit was dispensed to the subject between 2 visits, in a same way it will not be possible to determine the number of capsules taken, so protocol medication adherence taken will be set as missing. Unscheduled visits will be also included in the calculation if Drug Accountability eCRF Form is completed.

Cumulative NT-814 exposure (mg)	
It is assumed that on a day the subject takes the 4 planned capsules:
 
In Placebo group, Cumulative dose = 0
 
In NT-814 40mg group, Cumulative dose = <math>(\text{number of capsules taken} / 4) * 40 \text{ mg}</math>.
 
In NT-814 80mg group, Cumulative dose = <math>(\text{number of capsules taken} / 4) * 80 \text{ mg}</math>.
 
In NT-814 120mg group, Cumulative dose = <math>(\text{number of capsules taken} / 4) * 120 \text{ mg}</math>.
 
In NT-814 160mg group, Cumulative dose = <math>(\text{number of capsules taken} / 4) * 160 \text{ mg}</math>.

The following information will be tabulated overall and by treatment:

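### The SAP formula for duration of menopause has a misplaced bracket: it returns days labelled as years and puts every computed value in the top category

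*SAP*

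**What the plan says.** SAP 4.5.2 lists the variable for reporting by treatment group: "Duration of menopause (years) as continuous summary and in categories". The categories are under 5 years, 5 to under 10 years, and 10 years or more. The computation paragraph that follows gives the derivation: "Duration of menopause (y) = (Informed Consent date – Last menstrual period date) + 1/365.25".

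The same paragraph sets two conditions that matter here. After any imputation of a partial date, "the date of the last menstrual period must be more than 6 weeks prior to the date of Informed Consent (IC"). Where the date lacks a year, the subject gets no value: "If year is missing, no imputation will be done".

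The result goes into Table 14.1.3 of the study report (SAP 7.1). SAP 4.3.1 also has menopause characteristics summarised by treatment group at the interim analyses, with reference to the same derivation.

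**The concern.** By ordinary operator precedence the division applies only to the 1. The date difference is never converted, so the output is a day count plus 1/365.25, under a label that says years.

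A programmer who codes the line literally will produce a table with means in the hundreds or thousands of years and a single occupied category. That table could not show whether the five arms differ in the split between recent and long-standing menopause. A programmer who silently corrects the line will produce a sensible table that disagrees with its governing specification. Either way the text needs correcting.

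**Working it through.** The documents give no numeric value for this variable, so there is no figure of the plan's to reproduce. The check evaluates the formula as written and compares it with the bracketed form.

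**Inputs**
- Unit of a date difference: days, with +1 standing for one day. This is the SAP's convention in 4.2.8: "the study day is calculated as (date of assessment - date of the first randomised treatment intake date+ 1").
- Smallest admissible gap: more than 6 weeks before consent (SAP 4.5.2). More than 6 × 7 = 42 days means at least 43 days.
- Category limits: 5 and 10 years (SAP 4.5.2).
- A comparable conversion elsewhere: SAP Table 3 gives dosing duration in weeks as ("Last dose of randomised blinded treatment – first dose of randomised blinded treatment +1) / 7", with the +1 inside the bracket and the division applied to the whole.

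**Formulas**, with d the date difference in days:
- As written: W = d + 1/365.25 = d + 0.0027
- Bracket moved: F = (d + 1)/365.25

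| d (days) | W, as written | Category | F, bracket moved | Category |
|---|---|---|---|---|
| 43 | 43.003 | ≥10 | 0.120 | <5 |
| 365 | 365.003 | ≥10 | 1.002 | <5 |
| 1,095 | 1,095.003 | ≥10 | 3.001 | <5 |
| 2,556 | 2,556.003 | ≥10 | 7.001 | ≥5 to <10 |
| 3,651 | 3,651.003 | ≥10 | 9.999 | ≥5 to <10 |
| 3,652 | 3,652.003 | ≥10 | 10.001 | ≥10 |
| 5,478 | 5,478.003 | ≥10 | 15.001 | ≥10 |

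**Categories.** W reaches 10 once d ≥ 10 − 1/365.25 = 9.997, that is, from 10 days. The SAP's date check puts every computed gap at 43 days or more. Every subject with a value is therefore in the top category, and the other two are empty.

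**Continuous summary.** Substituting d = 365.25F − 1 gives W = 365.25F − 1 + 0.0027 = 365.25F − 0.9973. The standard deviation and any difference in means between arms are inflated by exactly 365.25. The mean is inflated by slightly less: the ratio W/F is 357 at 43 days, 364 at 365 days and 365 at 3,652 days.

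**Alternative reading.** If the date difference were already in years, adding 1/365.25 would add one day, and the formula would equal F exactly. The SAP states no such unit for this line, and its other date differences are in days.

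**The case against.** The strongest reply is that this is a slip whose intent is obvious. The line is labelled in years and uses the day-to-year constant, and the SAP brackets its dosing-weeks conversion correctly. A mean of several thousand years would be noticed at once, and nothing in the documents shows that any output was produced this way. That is fair, and it limits the practical risk. It does not make the rule right: no other place in the SAP restates the formula correctly, and the SAP is the document that defines the derivations.

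It can also be said that nothing of consequence depends on the variable. This stands:
- It is not a covariate. The models use treatment, baseline value and region, plus visit terms in the repeated-measures model (SAP 4.2.3, 4.6.1).
- It defines no subgroup or analysis set.
- SAP 4.3 bases the interim efficacy review on hot flush frequency and severity, and the safety review on adverse events and early withdrawals.
- Age at menopause onset has its own formula and is unaffected.

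The claim of hidden imbalance also has a limit. Because W is a linear function of F, the continuous summary would still show relative differences between arms and could be rescaled by hand. Only the category counts lose their information, and correct values should be recoverable from the subject listing of menopause characteristics (Listing 16.2.4.2).

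Finally, the relevant minimum gap is the SAP's date check. The eligibility criterion in Protocol 7.2, "at least 6 weeks postsurgical bilateral oophorectomy with or without hysterectomy", is time since surgery relative to Screening Visit 1 and is a different interval. The conclusion does not depend on which is used, since both far exceed 10 days.

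**Conclusion.** The formula is wrong as written. Followed literally, it reports days as years, with a mean about 365 times too large and every subject with a known year of last period in the category of 10 years or more. Subjects with a missing year have no value and are the only exception.

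This rests on two assumptions: that date differences are in days, as elsewhere in the SAP, and that the bracket as read is the bracket in the source. The line reads as one complete inline expression with its bracket closed, so a reading error is unlikely, and a glance at the source document would settle it.

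The point is minor. It concerns one descriptive baseline variable and has no bearing on the efficacy results, the adaptation decisions or the error rate.

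**What to change.** Replace the line in SAP 4.5.2 with:

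Duration of menopause (y) = (Informed Consent date − Last menstrual period date + 1) / 365.25

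Then confirm that the program behind Table 14.1.3 and Listing 16.2.4.2 uses this form, including for any interim output already delivered. The cost is one moved bracket and a short code check. No new data are needed and no other derivation changes.
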